9.3.2.2. Outcome Identification

Outcomes will be identified in participant data sources with algorithms based on codes for diagnoses, procedures, and treatments. Proposed algorithms and diagnostic codes for all prespecified outcomes will incorporate definitions developed by the ACCESS project⁴² and will be described in more detail in the statistical analysis plan (SAP). ACCESS developed harmonised definitions and code lists for the outcomes listed in **Table 1**. for application to routine healthcare data sources across Europe. These definitions were subsequently used for the calculation of background outcome rates to contextualize emerging COVID-19 vaccine safety data. Healthcare data covering approximately 130 million lives across 7 European countries and 22 data sources were used to generate background rates. Algorithms will be tailored to the data source and will consider the provenance of the medical records that have identified the outcome, e.g., primary care, access to hospital care, and access to emergency care.⁴³ Multiple algorithms for the same outcome may be included in the analysis, to assess the potential impact of differential misclassification. Several outcomes have been validated in previous VAC4EU studies.

Outcome onset will be primarily defined as the date of the healthcare encounter associated with the relevant diagnostic code. Most outcomes of interest are serious enough to warrant healthcare consultation close to the time of symptom onset. However, for those outcomes that might include a lag between the onset of symptoms and diagnosis in a healthcare setting (e.g., DVT or diabetes type 1), algorithms may incorporate additional considerations to capture onset dates closer to the time of symptom onset. These considerations will be detailed in the SAP. Sensitivity analyses may also be incorporated to assess assumptions around outcome onset for relevant outcomes.

9.3.3. Covariate Definitions

The following variables will be assessed at the date of vaccine administration (i.e, index date for the vaccinated cohort in the comparative cohort design and SCRI design) or matched index date (for the unvaccinated cohort in the comparative cohort design) or during the 12month baseline period. These variables will be used to further characterise the patient populations of interest and/or to control for confounding. The prespecified outcomes may

PFIZER CONFIDENTIAL CT24-WI-GL02-RF02 5.0 Non-Interventional Study Protocol Template For Secondary Data Collection Study 01-Aug-2023 Page 32 of 72 have different sets of risk factors, and outcome-specific analyses may contain different covariate sets. Covariates with sufficient availability across data sources include:

- Demographics
 - Age which may be categorised as age categories in line with published background incidence rates from ACCESS (60-64, 65-69, 70-79, 80+ years) dependent on sample size.
 - o Sex
 - Race and/or ethnicity, as appropriate in each country
 - Geographic region, as appropriate in each country
- Date of vaccination (categorised by month or year to assess trends in vaccine uptake)
- Comorbidities
 - History of anaphylaxis
 - History of allergies
 - Diabetes mellitus (types 1 and 2)
 - Hypertension
 - Cardiovascular disease
 - Cerebrovascular disease
 - Chronic respiratory disease (asthma, COPD, chronic bronchiectasis)
 - Haematological conditions
 - o CKD
 - Dementia (i.e, Alzheimer's disease and related disorders, senile dementia)
 - Chronic liver disease
 - o Cancer
 - Autoimmune disorders
 - Influenza infection or other respiratory infections
 - Charlson Comorbidity Index (may be included as the composite scale, or the scale components may be included as individual terms)
- Comedication use (prescriptions or dispensing, no over-the-counter medication use)
 - Analgesics
 - Antibiotics
 - Antiviral medications
 - Corticosteroids

PFIZER CONFIDENTIAL

CT24-WI-GL02-RF02 5.0 Non-Interventional Study Protocol Template For Secondary Data Collection Study 01-Aug-2023 Page 33 of 72

- o Non-steroidal anti-inflammatory drugs
- Psychotropics
- o Statins
- o Novel oral anticoagulants
- o Warfarin
- Number of medications used
- Healthcare utilisation
 - Number of hospitalisations
 - Number of emergency department visits
 - o Skilled nursing facility, nursing home, or extended care facility stay
 - Primary care utilisation
 - Cancer screening
 - Other preventive health services, as appropriate
- Other vaccinations
 - Seasonal influenza
 - o COVID-19
 - Pneumococcal (conjugate or polysaccharide)
 - o DTP
 - o TPV
 - o TV (MMR)
 - Haemophilus influenzae type b (Hib)
 - o HAV
 - o HBV
 - o VZV
 - o HZ
 - o HPV
 - Meningococcal (MenACWY or Meningitis B)
 - o Rotavirus

As feasible, the following covariates may also be considered pending confirmation of sufficient availability and completeness across participant data sources.

• Socioeconomic status (including social deprivation, housing, employment, and income, as feasible)

PFIZER CONFIDENTIAL

CT24-WI-GL02-RF02 5.0 Non-Interventional Study Protocol Template For Secondary Data Collection Study 01-Aug-2023 Page 34 of 72

- Residency in a long-term care facility
- Care setting of vaccine administration
- Personal lifestyle characteristics
 - o Smoking status
 - o BMI
- Surrogates of frailty
 - Wheelchair use
 - o Home hospital bed
 - o Paralysis
 - Parkinson's disease
 - o Skin ulcer
 - o Weakness
 - o Stroke/brain injury
 - Ambulance transport
 - o Dementia
 - Difficulty walking
 - Home oxygen
 - o Rehabilitation care
 - Psychiatric illness
 - o Sepsis
 - Heart failure
 - Podiatric care
 - o Bladder incontinence
 - Diabetes complications
 - o Arthritis
 - Coagulation deficiencies
 - o Vertigo
 - Lipid abnormalities
 - These may also be combined into a frailty index as an overall marker of ageing and vulnerability to poorer outcomes. For example, the eFI was developed using routine primary healthcare data to identify older people with mild,

PFIZER CONFIDENTIAL

CT24-WI-GL02-RF02 5.0 Non-Interventional Study Protocol Template For Secondary Data Collection Study 01-Aug-2023 Page 35 of 72 moderate and severe frailty and has shown robust predictive validity for outcomes of mortality, hospitalisation and nursing home admission.⁴⁴

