PFIZER GENERAL BUSINESS Staff must always refer to and follow the current official electronic document repository version. This document was created based on QMS04-GSOP-SD-GL06 9.0 CMCD Forms Template WORD 01-Nov-2021 Page 13 of 72 receive ABRYSVO compared to a relevant comparator group who does not receive ABRYSVO (evaluated as separate populations and if appropriate, as a combined population).

Study design

This is a retrospective, comparative cohort study using data access providers of the Vaccine Monitoring Collaboration for Europe (VAC4EU) that meet fit-for-purpose criteria. If appropriate, based on the outcome of interest, the study will also use a self-controlled risk interval (SCRI) design.

Population

The target population will consist of individuals who are immunocompromised, or renally or hepatically impaired (evaluated as separate populations and if appropriate, as a combined population) who are at least 60 years of age on the date of vaccination (i.e, index date for the vaccinated cohort) or on the matched index date (for the unvaccinated cohort), and who have at least 12 months of medical history in one of the data sources with no record of RSV vaccination in that 12 month period and who have at least one day of post-index follow up. Immunocompromised or renally impaired or hepatically impaired status will be ascertained via coded diagnoses, treatments, procedures, and/or laboratory values, as appropriate, at index date or in the 12-month baseline period prior to the index date.

Variables

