9.2.1.1. Immunocompromised Population

Individuals must meet at least one of the following criteria at index date or in the 12-month baseline period prior to the index date (unless otherwise specified) to be eligible for inclusion in the immunocompromised population. Definitions will be aligned as closely as possible across participant data sources. Definitions may be modified if certain data elements are not available or are incompletely captured in some data sources.

- Diagnosed with a primary immunodeficiency/immune dysregulation disorder, also known as inborn errors of immunity, as defined by the European Society for Immunodeficiencies (ESID) Registry,²⁴ at any point in medical history
- Diagnosed with HIV/AIDS
- Diagnosed with hematologic malignancy (e.g., chronic lymphocytic leukemia, non-Hodgkin lymphoma, multiple myeloma, acute leukemia) with evidence of treatment at any point in medical history
- Diagnosed with solid malignancy with evidence of treatment within the last 5 years
- Diagnosed with rheumatologic/inflammatory conditions (e.g., Sjogren's syndrome, SLE, psoriatic arthritis, rheumatic arthritis, arthritis spondylarthritis, polymyalgia rheumatica, demyelination multiple sclerosis, polymyalgia rheumatica, IBD, autoimmune thyroiditis) and have evidence of treatment with chemotherapy, immune modulators, or high-dose or long-term systemic corticosteroids (>3 months) in the last 12 months
- Solid-organ transplant recipients or islet transplant recipients taking immunosuppressive therapy
- CAR-T-cell therapy or hematopoietic stem cell transplant recipients taking immunosuppressive therapy
- Active treatment with various immunosuppressive agents (e.g., high-dose systemic corticosteroids [20 or more mg of prednisone or equivalent per day when administered for 2 or more weeks] or long term systemic corticosteroid use (>3 months), alkylating agents, antimetabolites, transplant-related immunosuppressive drugs, cancer chemotherapeutic agents classified as severely immunosuppressive, TNF blockers, and other biologic agents that are immunosuppressive or immunomodulatory, active treatment with ATC code L04).

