9.2.1.2. Renally Impaired Population

Individuals must have evidence of moderate or severe renal impairment, ascertained at index date or in the 12 months before index date using coded diagnoses and procedures or laboratory values as feasible.

In data sources where laboratory results are not available or where there are substantial levels of missingness, individuals with diagnosis codes that identify severe and moderate renal disease as part of the CCI by Ludvigsson et al²⁵ will be used. This includes but is not limited to:

PFIZER CONFIDENTIAL CT24-WI-GL02-RF02 5.0 Non-Interventional Study Protocol Template For Secondary Data Collection Study 01-Aug-2023 Page 25 of 72

- Hypertensive renal disease with renal failure
- Hypertensive heart and renal disease with renal failure
- Chronic nephritic syndrome
- Chronic tubulo-interstitial nephritis
- Chronic kidney disease (CKD)

Patients will be included in the renally impaired cohort if they have 2 different occurrences of those codes separated by at least 90 days in the baseline period. ICD-10 codes will be adapted to the specific disease coding system used in each data source.

In data sources where laboratory results are available (e.g., SIDIAP), individuals will also be included in the renally impaired cohort if:

- They have 2 eGFR test results < 60 mL/min/1.73 m²—taken from Levey et al²⁶ separated by at least 90 days (with no normal values in between) but not more than 540 days OR
- They have 2 UACR results \geq 30 mg/g separated by at least 90 days (with no normal values in between) and no more than 540 days (severe albuminuria)

Definitions for CKD stages are based on the KDIGO guidelines.^{26, 27} Currently, albuminuria levels are also used to stratify levels of renal impairment.²⁷ The 3 microalbuminuria categories add prognostic information on renal and cardiovascular complications to the eGFR categories. However, patients in eGFR categories 1 and 2 (eGFR \ge 60 mL/min/1.73 m2) and moderate albuminuria have a different clinical profile and normal to moderately increased risk of complications. Therefore, among patients with eGFR \ge 60 mL/min/1.73m² only the patients with severe albuminuria will be considered. A potential limitation of using UACR test results is that clinicians use dipstick measurements as the main method of assessing UACR, and dipstick measurements are not captured in most data sources.

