9.2.1.3. Hepatically Impaired Population

Individuals must have evidence of moderate or severe hepatic impairment, which will be ascertained at index date and in the 12 months before the index date using coded diagnoses and procedures or laboratory values as feasible.

In data sources where laboratory test results are not available, or where there are substantial levels of missingness, individuals will be considered in the target population if they have a diagnosis code that matches the category of moderate or severe hepatic disease according to the CCI revised by Glasheen et al³³ which has been shown to correlate with inpatient admissions and mortality rates. This definition includes but is not limited to:

- Oesophageal varices
- Gastric varices
- Alcoholic hepatic failure
- Toxic liver disease with hepatic necrosis
- Chronic hepatic failure
- Hepatic failure, unspecified
- Hepatic veno-occlusive disease
- Portal hypertension
- Hepatorenal syndrome

In addition, to maximize the inclusion of individuals with moderate or severe hepatic impairment, codes included in the adaptation of the CCI for mild liver disease by Ludvigsson et al²⁵ (e.g., viral hepatitis, autoimmune hepatitis) will be included if they coexist with an ascites code (R18).

In data sources where laboratory results are available (e.g., SIDIAP), severe chronic liver disease can be measured by a MELD score greater than 24.³⁴ The MELD score is calculated using serum bilirubin, serum creatinine, and International Normalized Ratio (INR) by the formula³⁵:

No exact correspondence exists between the Child-Pugh stages and the MELD scores. However, patients with MELD scores equal to or greater than 10 have similar mortality to patients with a Child-Pugh score of less than 10.²⁵ The same score threshold combined with elastography has clear prognosis implications for patients.³⁶ Thus, we propose to include in the study individuals with MELD scores equal to or greater than 10 to include additional individuals with moderate or severe hepatic impairment. Although there have been efforts to derive Child-Pugh scores from electronic healthcare data sources with identifiable rich clinical data,³⁷ those data may not be available in the data sources proposed for this study. PFIZER CONFIDENTIAL

CT24-WI-GL02-RF02 5.0 Non-Interventional Study Protocol Template For Secondary Data Collection Study 01-Aug-2023

```
Page 27 of 72
```

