9.3. Variables

9.3.1. Exposure Definition

Exposure will be based on recorded prescription, dispensing, or administration of ABRYSVO. Vaccine receipt and date of vaccination will be obtained from all available sources that capture ABRYSVO vaccination, such as pharmacy dispensing records, general practice records, immunization registers, vaccination records, medical records, or other secondary data sources. Depending on the data source, vaccines will be identified via

PFIZER CONFIDENTIAL CT24-WI-GL02-RF02 5.0 Non-Interventional Study Protocol Template For Secondary Data Collection Study 01-Aug-2023

Page 28 of 72

nationally used product codes where possible. The main exposure of interest is in the receipt of ABRYSVO.

- **CPRD Aurum (UK):** Data on vaccine exposure will be identified using CPRD Product Codes (PRODCODE ID's) and/or Medical Codes (MEDCODE ID's) based on available codes in CPRD product and medical dictionaries. Vaccination data originate from the patient primary care electronic medical records held within CPRD. The information captured at the individual patient level includes the name of the vaccine; manufacturing company; dose; stage of the vaccine schedule (if applicable); administration route; administration location (e.g., general practice); date of administration; and medical observations, events, referrals, test results, and prescribed medications recorded by the GP prior to, on, or after the vaccination date.
- VID (ES): Data on vaccine exposure are obtained from patient level electronic records within the vaccine information system which captures information on vaccine type, manufacturer, number of doses, location and administration date, adverse reactions related to vaccines, and if applicable, risk groups. Vaccines information in the VID is updated daily.
- **SIDIAP (ES):** Data are available on all routine childhood and adult immunizations, including the antigen and the number of administered doses. Vaccination information originates from patient electronic medical records. For each patient, SIDIAP has the date and centre of administration, dose, brand, reasons for vaccination (e.g., risk of group), and other information related to vaccination.
- **EpiChron (ES):** The EpiChron cohort provides data of individuals' pharmacotherapeutic history, including vaccination, with prescriptions and dispensation of drugs in community pharmacies, coded according to the WHO ATC classification system.

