9.3.1.1. Comparative Cohort Design

The exposure cohorts for the comparative cohort design will be defined as follows:

• The vaccinated cohort will be defined as individuals who were administered ABRYSVO.

To be included in the unvaccinated cohort, individuals must meet the following criteria:

• No vaccine record on index date: They must not have a record of receiving any vaccine, including the RSV vaccines, on the index date.

PFIZER CONFIDENTIAL

CT24-WI-GL02-RF02 5.0 Non-Interventional Study Protocol Template For Secondary Data Collection Study 01-Aug-2023 Page 29 of 72 • **No RSV vaccination in baseline period**: They must not have a record of receiving any RSV vaccine during the 12-month baseline before the index date.

Note: If individuals in the unvaccinated cohort receive ABRYSVO during the follow-up period, they will be censored in the unvaccinated cohort and become eligible for inclusion in the vaccinated cohort if all other eligibility criteria are met.

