a. Day 0 is the date of vaccine administration (i.e, index date for the vaccinated cohort in the comparative cohort design and SCRI design) or matched index date (for the unvaccinated cohort in the comparative cohort design) b. To align with ongoing postmarketing study C3671031, A Post-Authorization Safety Study of Guillain-Barré Syndrome (GBS) Following ABRYSVOTM Among Older Adults in the United States, sensitivity analyses will be performed for GBS, acute disseminated encephalomyelitis, and transverse myelitis using shorter risk intervals of 1-21 days, 5-28 days, and 1-21 days, respectively. Further details are outlined in Section 9.7.4. c. Published risk and control intervals for demyelinating diseases and cranial disorders were applied to transverse myelitis and narcolepsy/cataplexy.

d. Please note that alternative risk windows were reported in other studies.

e. To align with ongoing postmarketing study C3671037, A Post-Authorization Safety Study of Atrial Fibrillation Following Respiratory Syncytial Virus Vaccine (ABRYSVOTM) Among Older Adults in the

PFIZER CONFIDENTIAL

CT24-WI-GL02-RF02 5.0 Non-Interventional Study Protocol Template For Secondary Data Collection Study 01-Aug-2023

Page 31 of 72

Table 1	List of Select Adverse Events of Special Interest
---------	---

Body system/	Adverse event of special interest	Estimated risk	Analytic Approach
classification		window (days) ^a .	

Veterans Affairs Health System, sensitivity analysis will be performed for atrial fibrillation and supraventricular arrhythmias using a shorter risk interval of 0-3 days. Alternative risk intervals of 0-1 day or 0-30 days may also be considered. Details are provided in Section 9.7.4.

f. Similar risk and control intervals were applied to all cardiovascular and haematological disorders characterised by damage to the blood vessels and/or arteries and clotting (i.e, coagulation disorders and single organ cutaneous vasculitis).

g. Risk intervals for most outcomes start on Day 1 post-index, but for some outcomes, the risk interval starts on the day of vaccination due to biological plausibility of rapid onset following vaccination.

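### Population status and covariates may be read on the index date, which is a vaccination record in one cohort and an arbitrary calendar day in the other, so capture can differ between cohorts and a day-0 reaction can be adjusted for as baseline

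*Protocol*

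**What the plan says.** **Population status.** The Abstract sets the window as "at index date or in the 12-month baseline period prior to the index date". Section 9.2.1.1 repeats this for the immunocompromised: "Individuals must meet at least one of the following criteria at index date or in the 12-month baseline period prior to the index date". Section 9.2.1.3 has hepatic impairment "ascertained at index date and in the 12 months before the index date using coded diagnoses and procedures or laboratory values as feasible", and in sources without usable laboratory data one qualifying diagnosis code suffices. Section 9.2.1.2 also names the index date, but its code-based rule requires "2 different occurrences of those codes separated by at least 90 days in the baseline period".

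**Covariates.** Section 9.3.3 begins "The following variables will be assessed at the date of vaccine administration" and adds the matched index date for comparators and the 12-month baseline as alternatives. Its list includes history of anaphylaxis, cardiovascular disease, corticosteroids, emergency visits, hospitalisations and other vaccinations. Section 9.7.3.1 conditions the propensity score on characteristics as of the index date.

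**What day 0 is in each cohort.** For vaccinees it is the date of ABRYSVO administration (9.1). Comparators receive a date matched on calendar time, with no contact required, and section 9.3.1.1 adds: "They must not have a record of receiving any vaccine, including the RSV vaccines, on the index date".

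**Outcome windows.** Under Table 1, note g, for some outcomes "the risk interval starts on the day of vaccination due to biological plausibility of rapid onset following vaccination". These include anaphylaxis, generalised convulsion and death. Section 9.7.4 adds a 0-3 day analysis for atrial fibrillation and supraventricular arrhythmias.

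**A different window for utilisation.** Section 9.1.1 puts the healthcare utilisation used in the weights in the baseline period, defined as the 12 months before index.

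**The concern.** Day 0 gives the two cohorts unequal opportunities to be measured.

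- **Capture.** A vaccination contact is an occasion to record conditions and treatments. Section 9.3.1 says CPRD holds events, test results and prescriptions recorded by the GP on the vaccination date. A comparator need not have been seen that day.
- **Co-administered vaccines.** Other vaccinations are covariates under the same window. A vaccinee can have an influenza or COVID-19 vaccine recorded on day 0; a comparator, by rule, cannot.
- **Outcome read as baseline.** A post-injection emergency visit, corticosteroid prescription or anaphylaxis code on day 0 falls both inside the outcome window and inside the covariate window.

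ATT weighting makes comparators resemble vaccinees on recorded covariates. If true morbidity is recorded more completely in vaccinees alone, sicker comparators are weighted up, the comparator rate rises and the IRR falls. The balance checks in sections 9.7.1 and 9.7.3.1 use the same recorded covariates, so they cannot reveal this. None of the sensitivity analyses named in section 9.7.4 varies the covariate window.

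**Working it through.** **1. The plan's own figure.** Section 9.5 uses two-sided alpha 0.05, 80% power, 1:1 cohorts, an arrhythmia rate of 0.02 per person over 365 days, and IRR 2. For two Poisson rates, n = (z0.975 + z0.80)² (λ0 + λ1)/(λ1 − λ0)² = 7.849 × 0.06/0.0004 = 1,177.3, so 1,178 per cohort, as stated. This figure is not disputed; it is used in step 5.

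**2. Overlap of windows, from the text alone.** Section 9.2.2 removes anyone with the outcome diagnosis in the 12 months before index. Section 9.3.3 reads history of anaphylaxis on the index date or in those same 12 months. In the anaphylaxis analysis, therefore, an anaphylaxis diagnosis inside that covariate window could come only from day 0, which Table 1 counts as outcome time. A separate personal-history code or a longer look-back would be an exception.

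**3. Differential covariate capture (assumed inputs).** Let true prevalence p be equal in both cohorts, g the outcome rate ratio, s the baseline sensitivity in both, and d the share of missed cases captured on day 0 in vaccinees only.

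- Recorded prevalence in vaccinees: c = p[s + (1 − s)d]
- Relative rate among comparators without the record: r0 = [p(1 − s)g + (1 − p)]/(1 − ps)
- Weighted comparator rate: U = cg + (1 − c)r0
- Vaccinee rate with no true effect: V = pg + (1 − p)
- Factor on the IRR: V/U

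Example with p = 0.4, g = 3, s = 0.7, d = 0.5: c = 0.34; r0 = 0.96/0.72 = 1.333; U = 1.02 + 0.88 = 1.90; V = 1.80; factor 0.947.

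Over p = 0.2 or 0.4, g = 2 or 3, s = 0.7 or 0.9:

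| Missed cases captured on day 0 (d) | Factor on IRR |
|---|---|
| 5% to 10% | 0.989 to 0.999 |
| 25% | 0.973 to 0.996 |
| 50% | 0.947 to 0.992 |
| 0 (windows end on day -1) | 1.000 |

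**4. Differential entry (assumed inputs).** If a share f of vaccinees enters only through a day-0 code and has relative event rate h, the factor is 1 − f + fh.

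| f | h = 0.5 | h = 2 |
|---|---|---|
| 5% | 0.975 | 1.05 |
| 20% | 0.90 | 1.20 |

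The sign depends on whether these entrants are milder or sicker than the rest, which the documents do not say.

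**5. Effect on power at 1,178 per cohort, true IRR 2.** Power = Φ[(λ1 − λ0)/√((λ0 + λ1)/n) − 1.96].

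| Factor | Comparator rate held at 0.02, vaccinee rate = 0.04 × factor | Vaccinee rate held at 0.04, comparator rate = 0.02 / factor |
|---|---|---|
| 0.98 | 77.3% | 78.1% |
| 0.95 | 72.8% | 74.9% |

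The last column matches the mechanism in step 3. Neither column allows for the variance added by weighting.

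**The case against.** The strongest reply is that section 9.3.3 also offers the 12-month baseline, and that its list mixes items naturally read at index (age, vaccination date) with histories and counts naturally read over a look-back. Figure 1, note a, calls comorbidities, medications, vaccination and utilisation baseline conditions, and exact day offsets often go into a SAP. That is a fair reading of intent. But the protocol names the index date expressly for both status and covariates, and nothing excludes day-0 records.

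Several limits on the point stand:

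- **Entry.** Under the code-based renal rule a lone day-0 code cannot qualify. Many immunocompromised criteria also require treatment or duration.
- **Sources.** SNDS exposure is a pharmacy dispensing with no injection date (9.3.1, 9.4.5), so day 0 there need not be a clinical contact.
- **Vaccination-record fields.** Section 9.3.1 says "SIDIAP has the date and centre of administration, dose, brand, reasons for vaccination (e.g., risk of group"), and VID holds risk groups. These are listed as exposure fields; nothing says they define status or covariates.
- **Size.** Day 0 is one day added to a year in people with chronically managed disease, and Table 2 targets IRRs of 2 to 10.
- **Other checks.** Anaphylaxis and convulsion also have an SCRI analysis, which uses no propensity weights. Negative controls and quantitative bias analysis are under consideration.

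A reader might infer that the vaccination visit itself adds one primary care contact to every vaccinee's utilisation count. Section 9.1.1 does not support this, since it places utilisation used in the weights before index. It also requires a prior-year vaccination record of comparators, which works against a one-sided inflation of vaccinees' contacts.

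**Conclusion.** The rule as written permits differential capture of comorbidity, comedication and co-administered vaccines. For outcomes with a day-0 window, it also permits a post-vaccination event to be adjusted for as baseline. Both follow from the text.

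The size rests on assumption. For one covariate the factor on the IRR is roughly 0.95 to 1.00, reaching the low end only if day 0 captures about half of what a year of records missed. The covariate effect is probably toward a lower IRR; the entry effect can go either way. The day-0 outcome overlap is not quantified and should involve few people.

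A reader might go further and conclude that the design masks harm. The documents do not support that: they give no capture rates, the entry effect has no fixed sign, and the plausible effect of one covariate is small. What holds is that harm could be understated in some analyses, to a degree that varies by source and population and that the planned balance tables would not show.

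**What to change.** In the Abstract and sections 9.2.1.1 to 9.2.1.3 and 9.3.3, end the windows for population status and all time-varying covariates (comorbidities, comedication, utilisation, other vaccinations, frailty) on day -1 in both cohorts. Keep longer look-backs where specified, also ending on day -1. Use the index date only for age, sex, region, calendar date and the exposure record, including care setting of administration. Align the phrase in section 9.7.3.1 on characteristics as of the index date, and make section 9.3.3 match section 9.1.1 on utilisation.

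Same-day vaccines in vaccinees can be described as a feature of the exposure; weighting cannot balance them, because no comparator can have one.

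The cost is wording in these sections and a date offset in the centrally developed R script. People whose qualifying condition is first coded on the index date would not be included, which is likely a small loss in chronically managed populations. The per-cohort requirement of 1,178 in Table 2 does not change.
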